5.2 Secondary Endpoints

Secondary endpoints will include:

5.2.1 Overall survival (OS): Defined as time from the first dose of administration to death from any cause.

5.2.2 Overall response rates: Defined as the composite endpoint of response to treatment which includes Complete Response (CR), Partial Response (PR), stable disease (SD) as defined in International Response Criteria. We will also analyze Complete Response rate.

5.2.3 Univariate analysis of the risk of progression/relapse and mortality: In addition, multivariate analysis of the risk of progression/relapse and overall mortality will be conducted to assess influence of variables measured after the start of treatment.

5.2.4 Regimen-related toxicity: Graded and presented in a descriptive nature.

Descriptive analysis of baseline characteristics and demographics in this two-treatment arms study will be performed in the following manner. Continuous measurements will be summarized as mean (SD) or median (inter-quartile range) based on whether or not the data come from a normal distribution as validated by Shapiro-Wilks test of normality. Categorical measurements will be summarized as frequency (percentage). Proportion of overall survival will be estimated by the Kaplan-Meier product limit method. The univariate probability of the relapse and treatment-related mortality (TRM) will be calculated using cumulative incidence function.

5.3 Accrual, Registration and Follow-up

The targeted sample size is 54 subjects. It is estimated that four years of accrual will be necessary to enroll this number of subjects. About 50 patients (49-52) underwent allogeneic transplantation at this center, indicating that an appropriate number of subjects will be available to complete this study in the time frame anticipated. Subjects will enroll uniformly over the accrual period. The randomization will be stratified by relapse risk status (high versus low). Low relapse will include: AML CR1 and CML chronic phase. All other AML, MPD and MDS patients will be considered high relapse risk. An AML CR1 patient with a history of MDS will be considered high relapse risk. All patients who are Flt3/ITD positive at any time will be considered high relapse risk. Upon establishing eligibility, subjects will be randomized in equal numbers to the FluBu and FluBuTBI arms using permuted blocks within strata.

All subjects will be followed for one year from time of transplantation, during which they will be monitored for the effects of treatment through regular clinic visits. Additional follow-up data beyond one year of progression-free survival will be obtained from HUMC Cancer Center Database.

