3.10.1 Conditioning Regimens

Eligible patients who have signed informed consent will be randomized to treatment arm A (Flu-Bu) or treatment arm B (Flu-Bu-TBI).

3.10.2 Treatment arm A:

- 3.10.2.1 Patients must be admitted to HUMC prior to the start of the fludarabine and will not be discharged until engraftment has occurred.
- 3.10.2.2 Fludarabine will be administered at a dose of 40/mg/m² IV daily for 4 days starting on transplant day -6.
- 3.10.2.3 Busulfan will be administered immediately following the fludarabine at a dose of 130 mg/m² IV daily for 4 days starting on transplant day -6.
- 3.10.2.4 Patients will also receive rabbit antithymocyte globulin (Thymoglobulin) at a dose of 0.5 mg/kg IV on day -3, and 1.5 mg/kg on day -2 and 2 mg/kg on day -1
- 3.10.2.5 Hematopoietic cells will be infused on day 0
- 3.10.2.6 Graft versus host disease (GVHD) prophylaxis will consist of tacrolimus 0.03 mg/kg (or 0.015 mg/kg for age \geq 65) using ideal body weight, IV total daily dose starting on transplant day -2 and adjusted based on blood levels. Methotrexate at a dose of 5 mg/m² IV will be administered on transplant days +1, +3, +6 and +11
- 3.10.2.7 Dose adjustment for the fludarabine, busulfan and antithymocyte globulin will be as follows:
 - 3.10.2.7.1 If patient weighs less than 100% of ideal body weight (IBW), dosing is based on actual body weight
 - 3.10.2.7.2 If patient weighs 120-150% of IBW, dosing is based on adjusted body weight (ABW)
 - 3.10.2.7.3 If patient weighs greater than 150% of IBW, actual weight will be capped at 150% of ideal body weight, and this will be used in the adjusted body weight formula
- 3.10.2.8 Corrected body weight formula: ABW= IBW + [(0.25) x (actual BW-IBW)]

3.10.3 Treatment arm B:

- 3.10.3.1 Patients must be admitted to HUMC prior to the start of the fludarabine and will not be discharged until engraftment has occurred.
- 3.10.3.2 Fludarabine will be administered at a dose of 40/mg/m² IV daily for 4 days starting on transplant day -6.
- 3.10.3.3 Busulfan will be administered immediately following the fludarabine at a dose of 130 mg/m² IV daily for 4 days starting on transplant day -6.
- 3.10.3.4 Total body irradiation will be given in 2 fractions of 200 CGY (total 400 CGY) on day -1.

3.10.3.5 All patients in treatment arm B will also receive rabbit antithymocyte globulin (Thymoglobulin) at a dose of 0.5 mg/kg IV on day -3, and 1.5 mg/kg on day -2 and 2 mg/kg on day -1.

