5 STATISTICAL EVALUATION

5.1 Primary Objective

The primary objective of this single institution randomized Phase III trial is to compare the 1-year relapse rate of myeloid malignancy in patients receiving two different conditioning regimens. In this study, subjects will be randomly assigned to one of 2 conditioning regimens: fludarabine and busulfan or fludarabine, busulfan and low-dose total body irradiation. The myeloid malignancies include acute myeloid leukemia (AML), chronic myeloid leukemia (CML) and other myeloproliferative diseases, and myelodysplastic syndromes (MDS).

Primary endpoint will be the 1-year event free survival (EFS) for the two treatment groups, where the event is relapse or progression. Patients are considered a failure with respect to EFS if they experience disease relapse or progression. The time to this event is the time from transplant to relapse or progression. Subjects alive without confirmed disease progression will be censored at the time of last disease evaluation. Patients who die without evidence of disease relapse or progression will be censored at time of death and death will not be treated as failure for analysis of this primary endpoint.

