5.7 Primary Endpoint

The primary analysis will include all randomized subjects, classified according to their randomized treatment allocation by the *intent-to-treat* principle. The analysis of relapse or disease progression is planned at one year after accrual is completed. The two regimen arms will be compared utilizing a one-sided log rank test stratified on risk status, and using a level significance level of 0.05.

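### The primary analysis takes all randomized subjects but its clock starts at transplant, so a subject randomized and not transplanted has no valid primary time

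*Combined protocol and SAP*

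**What the plan says.** Four provisions of the combined protocol and SAP bear on this.

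- **When subjects are allocated.** 5.3: "Upon establishing eligibility, subjects will be randomized in equal numbers to the FluBu and FluBuTBI arms". Section 3.10.1 likewise randomizes patients who are eligible and have consented. Neither ties allocation to a transplant day.
- **Who is analysed.** 5.7: "The primary analysis will include all randomized subjects, classified according to their randomized treatment allocation", on the intent-to-treat principle.
- **When the primary clock starts.** 5.1: "The time to this event is the time from transplant to relapse or progression". Subjects alive without progression are censored at their last disease evaluation, and deaths without relapse are censored at death. Section 5.3 also counts the year of follow-up from transplantation.
- **When the arms diverge.** Both arms begin the same conditioning on day -6: "Busulfan will be administered immediately following the fludarabine at a dose of 130 mg/m² IV daily for 4 days starting on transplant day -6". Arm B adds only irradiation: "Total body irradiation will be given in 2 fractions of 200 CGY (total 400 CGY) on day -1".

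Sections 5.8.4 (secondary event-free survival) and 5.8.2 (overall survival) count time from randomization. The list entries for overall survival in 5.2.1 and 5.8.1.2 use first dose instead. Section 5.9.2 lets some subjects withdrawn after assignment be replaced.

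**The concern.** The analysis set is fixed at one moment and the time origin at a later one. A subject who enters the set but never reaches the origin cannot be placed on the time axis. The software will drop such a subject, or someone will have to improvise a rule after the fact.

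What is at stake is the meaning of the primary comparison. Intent-to-treat protects it because membership is settled by randomization. If membership depends in practice on reaching infusion, it depends on events and decisions after allocation. With no masking described, the decision to proceed, withdraw or replace a subject can be taken with the arm known. The trial is small, so a few subjects matter.

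**Working it through.** **Step 1. Apply the rules to a subject who is randomized and not infused.**

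| Rule | Result for this subject |
|---|---|
| 5.3 and 3.10.1, allocation | Randomized and assigned to an arm |
| 5.7, analysis set | Included |
| 5.1, time = event date minus transplant date | Undefined, as there is no transplant date |
| 5.1, censoring at last evaluation or death | Also undefined, for the same reason |
| 5.3, one year from transplantation | Undefined |
| 5.4, 10% dropout | Sizes the trial; gives no time zero |
| 5.9.2, replacement | Gives no time zero; silent on whether the replaced subject stays in the set |
| 5.8.4 and 5.8.2, time from randomization | Valid time |

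If a subject progresses and is infused later, the 5.1 time is negative. In neither case does the subject contribute an event or time at risk to the primary log-rank test.

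**Step 2. Reproduce the plan's sample size.** Inputs from 5.4: 1-year relapse 34% and 13.6%, one-sided 5%, 4 years' accrual, 1 year of follow-up, 10% dropout. Assumptions: exponential times, and dropout read as an annual loss, λ = -ln(0.90) = 0.1054.

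- Hazards: -ln(0.66) = 0.4155 and -ln(0.864) = 0.1462. HR = 0.352, |ln HR| = 1.045.
- Events for 80% power (Schoenfeld): 4(1.645 + 0.842)²/1.045² = 22.7, so 23.
- Event probability with 1 to 5 years of follow-up: h/(h+λ) × [1 - (e^-(h+λ) - e^-5(h+λ))/(4(h+λ))] = 0.599 (FluBu) and 0.296 (FluBuTBI), mean 0.447.
- N = 22.66/0.447 = 50.6, so 51.
- At N = 52: 23.3 events, power Φ(1.045 × √(23.3/4) - 1.645) = 80.9%. A Lakatos-type calculation gives 79.1%.

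The stated 52 subjects and 80.06% are reproduced. This point contradicts no figure in 5.4.

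**Step 3. Remove subjects who are never transplanted.** Their share is not in the documents. Take 3% to 10% as an assumption: 54 × 0.03 = 1.6 and 54 × 0.10 = 5.4 subjects. The table shows 0% to 15%, with the 10% annual loss applied on top.

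| Not transplanted | Subjects of 54 | Expected events | Power, Schoenfeld | Power, Lakatos | Randomized to obtain 52 transplanted |
|---|---|---|---|---|---|
| 0% | 0 | 24.2 | 82.2% | 80.4% | 52 |
| 5% | 2.7 | 23.0 | 80.4% | 78.6% | 52/0.95, so 55 |
| 10% | 5.4 | 21.7 | 78.5% | 76.7% | 52/0.90, so 58 |
| 15% | 8.1 | 20.5 | 76.5% | 74.6% | 52/0.85, so 62 |

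Each 5% costs about 2 points. The enrolment cap is 54.

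**Step 4. See what early allocation provides.** The fludarabine, busulfan, antithymocyte globulin and tacrolimus text is the same in 3.10.2 and 3.10.3. The irradiation is on day -1 in 3.10.3.4. Table 1, as it reads in the available text, marks it under day 0; this may be a layout fault, and if it is not, the two places must be reconciled. On either reading the regimens do not differ before day -1.

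**The case against.** The best defence is that this is a narrow gap that rarely bites. Much of it stands.

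- **The wait is probably short.** Section 3.4 requires the pre-transplant evaluation within 30 days of transplantation, and the organ-function criteria depend on those tests. A suitable donor is already an inclusion criterion (3.2.1.3). Sections 3.10 and 3.10.1 describe clearance, then admission, then allocation. A reader might infer an unlimited wait, or allocation before admission, but the text states neither. The moment of randomization is simply not fixed relative to clearance or day -6.
- **Most of the analysis is unaffected.** A reader might infer that the primary analysis cannot be run, or that these subjects can have no outcome. Both go too far. The test runs on all transplanted subjects. An untransplanted subject can progress; that event merely has no valid time from transplant. Secondary event-free survival and the 5.8.2 overall survival capture such subjects.
- **Attrition is partly provided for.** The 10% dropout and the replacement rule may restore numbers, and if the 10% was meant to include these subjects the power loss is smaller. Neither supplies a time zero, and replacement without a rule for the replaced subject sits badly with intent-to-treat.
- **No selection bias is shown.** Identical treatment up to day -1 means the assigned regimen cannot itself cause earlier deaths or progressions. Dropout that depends on the assignment is possible without masking, but nothing in the documents shows it.
- **The stated aim in 5.5 is relapse after transplantation.** A clock from randomization departs slightly from that.

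The defence does not remove the conflict itself: 5.7 names a population for which 5.1 defines no time.

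**Conclusion.** The conflict between 5.7 and 5.1 is real and should be resolved before analysis. Followed as written, the rules turn the named intent-to-treat comparison into one of transplanted patients and leave relapse or progression before infusion uncounted.

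The size is uncertain and may be small: about 2 to 5 of 54 subjects if 3% to 10% are not transplanted, and about 2 points of power per 5% lost. This rests on the assumed non-transplant share and on the plan's 1 to 5 years of event collection. Whether that follow-up basis fits a 1-year endpoint is a separate question.

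Two larger-looking figures should not be used. Applying the 34% control rate to a 14- or 30-day wait gives 54 × (1 - 0.66^(14/365)) = 0.9 or 54 × (1 - 0.66^(30/365)) = 1.8 early progressions, but that is a post-transplant rate carried to a period for which the documents give none. The binomial chance that the arms differ by two or more untransplanted subjects is 21% to 49% at 3% to 10%, but that is chance imbalance under equal rates and does not measure bias.

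**What to change.** - **5.1:** measure time to relapse or progression from randomization, and count relapse or progression before infusion as an event.
- **5.7 and 5.9.2:** keep every randomized subject in the primary set, including any who are replaced. Report by arm the subjects not transplanted.
- **5.3:** state that randomization follows final patient and donor clearance, as close to the start of conditioning as practicable. Match the follow-up wording, so that a subject not transplanted also has a defined follow-up period.

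Changing the time origin alone removes the contradiction and brings the primary endpoint into line with 5.8.4 and 5.8.2. Late randomization keeps the number affected low.

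The cost is amendment wording, with no added subjects. The primary clock will include a short pre-transplant interval; time from transplant can be kept as a sensitivity analysis. Randomizing late also means holding provisional irradiation slots, about half of which would be released under 1:1 allocation.

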5.4 Sample Size and Power Calculations

The main objective is to compare the relapse-free surviving proportions at 1 year in myeloid malignancy patients who are randomized to either FluBuTBI or FluBu conditioning regimen.

In examining the time to relapse, we consider an analysis of the proportion surviving without relapse/progression at the 1 year endpoint. A comparison of this event between the two treatment arms will be conducted using log-rank test statistics at the 5% level of significance. Based on this statistic, the calculation of sample size was obtained using PASS 2008. According to the results from previous studies [De Lima et al], the 1-year relapse rate in patients with myeloid malignancies being treated with FluBu is 34%. We posit that when the FluBuTBI regimen is used the relapse rate will be reduced to 13.6%, which is 40% of the relapse risk in the FluBu regimen arm. Then, a one-sided log-rank test will be used to examine evidence for a reduction in disease relapse. For the nominal power of 80%, significance level of 5%, 4 year accrual, 1 year follow-up and 10% drop out rate in both FluBuTBI and FluBu treatment arm, 52 patients (26 per arm) will be required to detect the 20.4 difference (60% reduction in relapse rate). This calculation achieved 80.06%. To adjust for balanced samples within the risk status, the study will enroll a maximum of 54 patients (27 per arm).

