2.1 Primary Objective

The primary objective is to compare the relapse rate at 1 year of patients with myeloid malignancies receiving each regimen.

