3 INVESTIGATIONAL PLAN

3.1 Overall Design and Plan of Study

This is a single institution study of fludarabine and busulfan versus fludarabine, busulfan and low dose total body irradiation in patients undergoing allogeneic stem cell transplantation. A study population of 54 subjects will be enrolled from The John Theurer Cancer Center at Hackensack University Medical Center. Subjects who are eligible to receive allogeneic hematopoietic stem cell transplantation according to the eligibility criteria will be consented and enrolled. Subjects will be randomly assigned to receive one of 2 conditioning regimen: fludarabine and busulfan, or fludarabine busulfan and low dose total body irradiation (TBI). Subjects will be followed until 1 year post transplantation to assess the relapse rate in each arm and transplant-related toxicity

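### The 80.06% power assumes 1 to 5 years at risk per patient; for the 1-year relapse endpoint, 26-27 per arm gives about 12-13 relapses and about 53-56% power

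*Combined protocol and SAP*

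**What the plan says.** The 1-year horizon runs through the plan:

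- Section 2.1: the aim is to "compare the relapse rate at 1 year of patients with myeloid malignancies receiving each regimen".
- Section 3.1: "Subjects will be followed until 1 year post transplantation to assess the relapse rate in each arm".
- Section 5.1: "Primary endpoint will be the 1-year event free survival (EFS) for the two treatment groups, where the event is relapse or progression".
- Section 5.3: "All subjects will be followed for one year from time of transplantation".
- Section 5.4: "we consider an analysis of the proportion surviving without relapse/progression at the 1 year endpoint".
- Section 5.6: the hypothesised rates, 34% and 13.6%, are 1-year rates.

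The power statement in 5.4 is that "52 patients (26 per arm) will be required to detect the 20.4 difference (60% reduction in relapse rate). This calculation achieved 80.06" per cent. Its inputs, besides a one-sided 5% log-rank test, are "4 year accrual, 1 year follow-up and 10% drop out rate in both FluBuTBI and FluBu treatment arm". The enrolment target is then raised to 27 per arm.

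Other text leaves the window of the test open. Section 5.1 says "Subjects alive without confirmed disease progression will be censored at the time of last disease evaluation", with no cut at 1 year. Section 5.3 draws later follow-up from an institutional database. Section 5.7 places the analysis a year after the last patient is enrolled.

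**The concern.** In a log-rank power calculation, accrual time plus follow-up time sets how long patients are at risk. With uniform accrual over 4 years and 1 more year of follow-up, the first patient contributes 5 years and the last contributes 1. Power depends on the number of relapses, so the calculation credits the trial with relapses in years 2 to 5. A comparison at 1 year cannot use those.

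If the test is the 1-year comparison, a true 60% reduction would be missed almost half the time, yet a negative result would be read against a claimed 80% power. If the test uses all follow-up, the 80% belongs to a different endpoint, and about half of its events come after scheduled disease assessment has ended. With the window unspecified, it could also be chosen after the data are seen.

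**Working it through.** **Inputs.** From 5.4: 1-year relapse of 34% (FluBu) and 13.6% (FluBuTBI), one-sided 5%, 26 per arm (27 enrolled), 4-year accrual, 1-year follow-up, 10% dropout. From 5.3: uniform accrual and equal allocation. Section 5.4 gives no time unit for dropout; 10% per year is an assumption, and no dropout is shown beside it.

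**Hazards.** FluBu: −ln(0.66) = 0.4155 per year. FluBuTBI: −ln(0.864) = 0.1462 per year. Hazard ratio 0.1462/0.4155 = 0.352, with log −1.0447. Dropout of 10% per year: δ = −ln(0.90) = 0.1054.

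**Events needed for 80% power.** 4(1.645 + 0.842)² / 1.0447² = 22.7.

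**Reproducing the plan's figure.** With s = λ + δ and 1 to 5 years at risk, the probability of an observed relapse is (λ/s) × [1 − (e^(−s) − e^(−5s))/(4s)].

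- FluBu: 0.599. FluBuTBI: 0.296.
- Expected relapses: 26 × (0.599 + 0.296) = 23.3.
- Schoenfeld power: Φ(√23.27 × 1.0447/2 − 1.645) = Φ(0.875) = 80.9%.
- Simulation (40,000 log-rank tests): 79.1%.

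These two values bracket 80.06%.

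**The same design with 1 year at risk per patient.** The probability of an observed relapse becomes (λ/s)(1 − e^(−s)). Without dropout this is simply 0.34 and 0.136, so 26 × 0.476 = 12.4 and 27 × 0.476 = 12.9 relapses. With dropout it is 0.324 and 0.129.

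| At risk | Per arm | Dropout | Relapses | Schoenfeld | Simulated log-rank |
|---|---|---|---|---|---|
| 1 to 5 years | 26 | none | 26.6 | 85.3% | 84.0% |
| 1 to 5 years | 26 | 10%/year | 23.3 | 80.9% | 79.1% |
| 1 year | 26 | none | 12.4 | 57.6% | 54.7% |
| 1 year | 26 | 10%/year | 11.8 | 55.9% | 53.3% |
| 1 year | 27 | none | 12.9 | 59.0% | 55.5% |
| 1 year | 27 | 10%/year | 12.2 | 57.2% | 54.3% |

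The reproduced design therefore takes 23.3 − 11.8 = 11.5 of its relapses (49%) from after year 1.

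**Sensitivity of the 1-year figure.**

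- Across Schoenfeld, Freedman, Lakatos and two-proportion calculations, 26-27 per arm gives 50-59%.
- Stratified log-rank, 27 per arm: 54-58%, assuming a low-risk share of 19-48% and a low-to-high hazard ratio from 1 to 0.25.
- Simulated type I error of the capped test is 5.2%, so a conservative test does not explain the low power.
- With 27 per arm, 80% power at 1 year needs FluBuTBI relapse of about 7-8%. Simulated power is 83.3% at 7.0% and 79.4% at 8.0% without dropout, and 81.1% and 77.4% with 10% per year.

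**Sensitivity of the uncapped figure.** The 80% needs the first-year hazard to persist to year 5. If the hazard after year 1 falls to three-quarters, half or a quarter of its first-year value (assumed multipliers), power with 27 per arm and 10% per year dropout is 77%, 71% or 65%.

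**The case against.** The best defence is that nothing in the plan truncates the log-rank test at 1 year. Censoring at the last disease evaluation, the database follow-up and the timing of the analysis all fit an uncapped test. The overall survival and event-free survival tests in 5.8.2 and 5.8.4 run to the end of the study and are described as parallel to the relapse analysis. On that reading the 80% matches the planned test, and the fault is loose use of the 1-year label.

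The text does leave this reading open. It does not rescue the power statement, because 5.4 attaches the 80% to a 20.4-point difference in 1-year rates and an uncapped test is not a test of that difference. It would also rely on relapses after the last scheduled visit (12 months, section 3.7) and the last scheduled marrow (one year, section 3.8), found only when relapse is suspected. The timing in 5.7 suits a capped test equally well, since the last patient needs a year.

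Three narrower points have some force:

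- **Dropout.** The unit is unknown, and other formulas reach about 80% with no dropout (Freedman 79.7%, Lachin-Foulkes 80.8%). The dropout attribution is therefore uncertain, but each of these routes still needs 1 to 5 years at risk.
- **Deaths without relapse.** Section 5.1 censors them, and 5.10 assumes 10% non-relapse mortality on FluBu. If 34% and 13.6% are risks in the absence of death, and 10% of both arms die within 3 months (assumed), 1-year power at 27 per arm falls to 51-54%. If they are cumulative incidences, the no-dropout counts above stand.
- **Marrow window.** Section 3.8 allows the one-year marrow 30 days either way, so a strict 365-day cut would lose relapses found at a compliant visit. Extending the cut to day 395 gives 27 × (0.362 + 0.146) = 13.7 relapses without dropout and Schoenfeld power of 61%, still far from 80%.

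**Conclusion.** The concern holds. The stated 80.06% does not apply to the 1-year comparison to which 5.4 attaches it. On that horizon the planned 26-27 per arm has about 53-56% power for 34% versus 13.6%, with about half of the 22.7 events needed. This rests on the plan's own rates, proportional hazards, and dropout between none and 10% per year. The choice of formula, stratification and censored deaths move the figure by a few points and never bring it near 80%.

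If the uncapped test is intended, about 80% is attainable, but only for time to relapse over all follow-up and only if the first-year hazard continues to year 5. The plan does not choose between the two, so the sole justification for the sample size is wrong as written. It must be corrected.

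**What to change.** Choose one window and make 5.1, 5.3, 5.4 and 5.7 agree with it.

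- **If the 1-year comparison is primary:** state in 5.7 that the stratified log-rank test is truncated at 1 year, worded so that a relapse found at a marrow within the permitted 30 days still counts. In 5.4, state that 27 per arm gives about 55% power for 34% versus 13.6%, and about 80% only if FluBuTBI relapse is about 7-8%. Say how dropout and deaths without relapse were handled.
- **If all follow-up is primary:** relabel the endpoint as time to relapse or progression over all follow-up. State in 5.4 that the 80% assumes 1 to 5 years at risk and a constant hazard, and withdraw the claim that it applies to the 1-year rate.

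The cost is protocol wording only. No patients are added. The price is either a less favourable stated power or a primary endpoint that is no longer the 1-year rate.
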